6.5.4.1 Infusion-related Reactions

Infusion-related reactions, including hypersensitivity, are defined in this section.

A. Symptoms:

- Fever
- Chills
- Rigors
- Diaphoresis
- Headache

B. Management (see [Table 6](#))

Table 6 Treatment Modification for Symptoms of Infusion-related Reactions Caused by MSB0011359C

NCI-CTCAE Grade	Treatment Modification for MSB0011359C
Grade 1 – mild 
• Mild transient reaction; infusion interruption not indicated; intervention not indicated.	
• Decrease the MSB0011359C infusion rate by 50% and monitor closely for any worsening.• The total infusion time for MSB0011359C should not exceed 120 minutes
Grade 2 – moderate 
• Therapy or infusion interruption indicated but responds promptly to symptomatic treatment (for example, antihistamines, NSAIDs, narcotics, IV fluids); prophylactic medications indicated for ≤ 24 hours.	
• Stop MSB0011359C infusion.• Resume infusion at 50% of previous rate once infusion-related reaction has resolved or decreased to at least Grade 1 in severity, and monitor closely for any worsening
Grade 3 or Grade 4 – severe or life-threatening 
• Grade 3: Prolonged (for example, not rapidly responsive to symptomatic medication and / or brief interruption of infusion); recurrence of symptoms following initial improvement; hospitalization indicated for clinical sequelae.• Grade 4: Life-threatening consequences; urgent intervention indicated.	
• Stop the MSB0011359C infusion immediately and disconnect infusion tubing from the subject.• Subjects have to be withdrawn immediately from MSB0011359C treatment and must not receive any further MSB0011359C treatment

IV = intravenous; NCI-CTCAE = National Cancer Institute-Common Terminology Criteria for Adverse Event; NSAIDs = nonsteroidal anti-inflammatory drugs.

Additional Modifications for Subjects With Grade 2 Infusion-related Reactions

If, in the event of a Grade 2 infusion-related reaction that does not improve or worsens after implementation of the modifications indicated in Table 6 (including reducing the infusion rate by 50%), the Investigator may consider treatment with corticosteroids and the infusion of IMP should be stopped for that day. At the next infusion, the Investigator may consider the addition of H2-blocker antihistamines (for example, famotidine or ranitidine), in addition to premedication, for select subjects. However, prophylactic steroids are NOT permitted. If the subject has a second infusion-related reaction Grade ≥ 2 on the slower infusion rate, with or without the addition of further medication to premedication, the infusion should be stopped and the subject removed from MSB0011359C treatment.

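### Section 6.5.4.1 permits a next infusion after a Grade 2 reaction worsens on the halved rate, although Table 6 makes recurrence after improvement Grade 3 and bars further drug

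*Protocol*

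**What the plan says.** All the relevant text is in Protocol Section 6.5.4.1.

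**Table 6, Grade 2.** The definition includes a prompt response: "Therapy or infusion interruption indicated but responds promptly to symptomatic treatment". The action is to stop, and then: "Resume infusion at 50% of previous rate once infusion-related reaction has resolved or decreased to at least Grade 1 in severity".

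**Table 6, Grade 3.** The definition reads: "Prolonged (for example, not rapidly responsive to symptomatic medication and / or brief interruption of infusion); recurrence of symptoms following initial improvement". The action for Grades 3 and 4 is to stop and disconnect, and then: "Subjects have to be withdrawn immediately from MSB0011359C treatment and must not receive any further MSB0011359C treatment".

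**Paragraph after Table 6**, headed "Additional Modifications for Subjects With Grade 2 Infusion-related Reactions". It applies to a "Grade 2 infusion-related reaction that does not improve or worsens after implementation of the modifications indicated in Table 6", and it states that those modifications include the 50% rate cut. Corticosteroids may be considered, and "the infusion of IMP should be stopped for that day. At the next infusion, the Investigator may consider the addition of H2-blocker antihistamines". Removal from treatment comes later: "If the subject has a second infusion-related reaction Grade ≥ 2 on the slower infusion rate", whether or not anything was added to the premedication.

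**The concern.** The same clinical event can be read under two adjacent rules with opposite consequences. One ends treatment for good. The other ends it for the day and describes how the next infusion might be given. A site that takes the paragraph at its word could re-expose a subject whom Table 6 bars from the drug, so the error runs in the unsafe direction.

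The grade that the investigator settles on also has a procedural effect. Infusion-related reactions of any grade are adverse events of special interest (Section 3.5.1). Under Section 7.4.1.4, a nonserious one is reported within 24 hours at Grade 3 or above, and within 5 working days at Grade 1 or 2. That consequence is conditional: it arises only if the paragraph leads the site to leave the event at Grade 2.

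**Working it through.** No formula or planned figure is involved, so the check is a comparison of texts.

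**Step 1: what precedes the half rate.** For a Grade 2 reaction, Table 6 makes resolution, or a fall to Grade 1, the condition for restarting. A Grade 2 reaction that has reached the restart has therefore already improved.

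**Step 2: what Table 6 calls the next event.** If symptoms then recur, the Grade 3 recurrence criterion is met and the subject receives no more drug.

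**Step 3: what the paragraph calls it.** Its trigger includes worsening after the 50% cut. It keeps the label Grade 2 and foresees a next infusion.

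**Step 4: take each course separately.**

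- *Fell to Grade 1, restarted at 50%, worsened again.* This is inside the paragraph's trigger, and the natural reading of Table 6 is recurrence after improvement, hence Grade 3. The texts conflict.
- *Resolved, restarted at 50%, returned.* This is plainly recurrence under Table 6. The paragraph speaks of not improving or worsening, not of returning, so its application here is an inference, though a fair one. The texts conflict on that inference.
- *Fell to Grade 1, restarted at 50%, Grade 1 symptoms continued unchanged.* Nothing has recurred, so there is no conflict.
- *Began at Grade 1, slowed by 50% under the Grade 1 row, then rose to Grade 2 for the first time.* The subject is on the reduced rate without any earlier improvement, so the recurrence criterion is not met. There is no conflict.
- *Did not settle to Grade 1 after stopping and treatment.* This sits badly with the prompt response required for Grade 2 and resembles the example given for a prolonged Grade 3 reaction. But Table 6 then gives no restart, so it is not clear that the case reaches a paragraph that presupposes the rate cut. This is a matter of judgement.

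**Step 5: look for a rule of precedence.** Section 5.1.7.2 requires discontinuation for Grade 3 drug reactions, with exceptions that name no infusion-related reaction. It sends infusion reactions of every grade back to Section 6.5.4.1. Section 5.5.1 withdraws subjects at Grade 3 or above. Section 7.4.1.1 has investigators grade by NCI-CTCAE v4.03. Each of these depends on the grade, and none says when a reaction handled under the paragraph stops being Grade 2. Table 7, for immune-related events, does contain such instructions: a worsening event is to be treated as the higher grade. Section 6.5.4.1 has no counterpart.

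**The case against.** The best reply is that the paragraph is confined to Grade 2 by its heading and its text, that nothing forbids regrading, and that an event meeting a Grade 3 criterion falls under the mandatory Grade 3 row. An investigator who regrades will reach the right result. This stands as a reading, but the paragraph expressly takes in reactions that have worsened and gives no prompt to regrade them.

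Second, its last sentence can be read as covering the same day: a reaction that resolves and comes back at Grade 2 on the slower rate is arguably the second one, so the subject is removed, as Table 6 requires. That reading is open, since the only slower rate defined for a Grade 2 reaction is the same-day restart. However, the reference to additions to premedication points to the next infusion, so the sentence does not clearly settle the matter.

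Third, the paragraph orders no infusion. It says what may be considered at the next one, and Section 5.5.1 lets the investigator withdraw a subject for any adverse event. This stands fully. A reader might infer that at least one more infusion follows; the text only permits it.

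A reader might also infer that the whole paragraph contradicts Table 6, or that most reactions handled under it are really Grade 3. Step 4 shows courses with no conflict and one open to judgement, and the documents give no frequencies for any of them.

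Other safeguards soften the risk. Premedication must continue after a Grade 2 or higher reaction in the first two infusions (Section 3.5.1), and subjects are observed for 2 hours after each infusion (Section 6.5.4). Neither prevents the next infusion.

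**Conclusion.** The text is wrong as written: it contains an internal contradiction, limited to Grade 2 reactions that worsen or, by inference, return after a half-rate restart that itself required improvement. For those reactions Table 6 allows no further infusion, while the paragraph allows one without requiring it.

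The conclusion assumes that renewed worsening after a fall to Grade 1 counts as recurrence, and that the second-reaction sentence is not clearly a same-day rule. If a site reads that sentence as same-day, a recurrence at Grade 2 or above leads to removal under either text.

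This is a minor-to-moderate safety clarification. How many subjects would be affected cannot be estimated from the documents, and with last subject out planned for Q4 2021 the remaining exposure may be small. There is no effect on sample size, power or response endpoints, and no effect on reported event counts is claimed.

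**What to change.** Add to Section 6.5.4.1, after the Grade 2 paragraph:

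*Stopping for the day and continuing at the next infusion applies only while the reaction remains Grade 2 by Table 6. A reaction that meets any Table 6 Grade 3 criterion, including recurrence or worsening after the 50% restart following initial improvement, is graded 3 and follows the Grade 3 row. The rule on a second reaction at the slower rate also covers recurrence on the same day.*

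If the sponsor does intend to allow one rechallenge after such a reaction, it should instead amend the Grade 3 row of Table 6 and add the exception to Section 5.1.7.2, so that both places agree.

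The cost of the clarification is a few sentences and a letter to sites. It needs no extra procedures or subjects.

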6.5.4.2 Severe Hypersensitivity Reactions and Flu-like Symptoms

If a hypersensitivity reaction occurs, the subject must be treated according to the best available medical practice. A complete guideline for the emergency treatment of anaphylactic reactions according to the Working Group of the Resuscitation Council (United Kingdom) and can be found at <https://www.resus.org.uk/pages/reaction.pdf>. Subjects should be instructed to report any delayed reactions to the Investigator immediately.

A. Symptoms

- Impaired airway
- Decreased oxygen saturation (< 92%)
- Confusion
- Lethargy
- Hypotension
- Pale / clammy skin
- Cyanosis.

B. Management

1. Epinephrine injection and IV dexamethasone
2. Patient should be placed on cardiac, blood pressure, heart rate, and oxygen saturation monitor immediately
3. Alert intensive care unit for possible transfer if required.

For prophylaxis of flu-like symptoms, a NSAID, for example, ibuprofen 400 mg or comparable NSAID dose, may be administered 2 hours before and 8 hours after the start of each dose of MSB0011359C IV infusion.

6.5.4.3 Immune-Related Adverse Events

Since inhibition of PD-L1 stimulates the immune system, irAEs may occur.

Treatment of irAEs is mainly dependent upon severity (NCI-CTCAE grade):

- Grade 1 to 2: treat symptomatically or with moderate dose steroids, more frequent monitoring
- Grade 1 to 2 (persistent): manage similar to high grade AE (Grade 3 to 4)
- Grade 3 to 4: treat with high-dose corticosteroids.

Treatment of irAEs should follow guidelines set forth in [Table 7](#).

Table 7 Management of Immune-Related Adverse Events

Gastrointestinal irAEs		
Severity of Diarrhea / Colitis (NCI-CTCAE v4.03)	Management	Follow-up

Grade 1 Diarrhea: < 4 stools/day over Baseline Colitis: asymptomatic
	
Continue MSB0011359C therapy Symptomatic treatment (for example, loperamide)
	
Close monitoring for worsening symptoms Educate subject to report worsening immediately If worsens: Treat as Grade 2 or 3/4

Grade 2 Diarrhea: 4 to 6 stools per day over Baseline; IV fluids indicated < 24 hours; not interfering with ADL Colitis: abdominal pain; blood in stool
	
Delay MSB0011359C therapy Symptomatic treatment
	
If improves to Grade 1: Resume MSB0011359C therapy If persists > 5 to 7 days or recur: 0.5 to 1 mg/kg/day methylprednisolone or equivalent When symptoms improve to Grade 1, taper steroids over at least 1 month, consider prophylactic antibiotics for opportunistic infections, and resume MSB0011359C therapy per protocol. If worsens or persists > 3 to 5 days with oral steroids: Treat as Grade 3 to 4

Grade 3 to 4 Diarrhea (Grade 3): ≥ 7 stools per day over Baseline; incontinence; IV fluids ≥ 24 hours; interfering with ADL Colitis (Grade 3): severe abdominal pain, medical intervention indicated, peritoneal signs Grade 4: life-threatening, perforation
	
Discontinue MSB0011359C therapy per protocol 1 to 2 mg/kg/day methylprednisolone IV or equivalent Add prophylactic antibiotics for opportunistic infections Consider lower endoscopy
	
If improves: Continue steroids until Grade 1, then taper over at least 1 month If persists > 3 to 5 days, or recurs after improvement: Add infliximab 5 mg/kg (if no contraindication). Note: Infliximab should not be used in cases of perforation or sepsis Permanently discontinue IMP

Dermatological irAEs		
Grade of Rash (NCI-CTCAE v4.03)	Management	Follow-up
Grade 1 to 2 Covering \leq 30% body surface area	Symptomatic therapy (for example, antihistamines, topical steroids) Continue MSB0011359C therapy	If persists > 1 to 2 weeks or recurs: Consider skin biopsy Consider delaying MSB0011359C therapy Consider 0.5 to 1 mg/kg/day methylprednisolone IV or oral equivalent. Once improving, taper steroids over at least 1 month, consider prophylactic antibiotics for opportunistic infections, and resume MSB0011359C therapy If worsens: Treat as Grade 3 to 4
Grade 3 to 4 Covering > 30% body surface area; life-threatening consequences	Delay or discontinue MSB0011359C therapy Consider skin biopsy Dermatology consult 1 to 2 mg/kg/day methylprednisolone IV or IV equivalent	If improves to Grade 1: Taper steroids over at least 1 month and add prophylactic antibiotics for opportunistic infections Resume MSB0011359C therapy (except in cases of Toxic Epidermal Necrolysis or Stevens-Johnson Syndrome)
Pulmonary irAEs		
Grade of Pneumonitis (NCI-CTCAE v4.03)	Management	Follow-up
Grade 1 Radiographic changes only	Consider delay of MSB0011359C therapy Monitor for symptoms every 2 to 3 days Consider Pulmonary and Infectious Disease consults	Re-image at least every 3 weeks If worsens: Treat as Grade 2 or Grade 3 to 4
Grade 2 Mild to moderate new symptoms	Delay MSB0011359C therapy Pulmonary and Infectious Disease consults Monitor symptoms daily, consider hospitalization 1 mg/kg/day methylprednisolone IV or oral equivalent Consider bronchoscopy, lung biopsy	Re-image every 1 to 3 days If improves: When symptoms return to near Baseline, taper steroids over at least 1 month and then resume MSB0011359C therapy and consider prophylactic antibiotics If not improving after 2 weeks or worsening: Treat as Grade 3 to 4 Permanently discontinue IMP

Grade of Pneumonitis (NCI-CTCAE v4.03)	Management	Follow-up
Grade 3 to 4 Severe new symptoms; New / worsening hypoxia; life-threatening	Discontinue MSB0011359C therapy Hospitalize Pulmonary and Infectious Disease consults 2 to 4 mg/kg/day methylprednisolone IV or IV equivalent Add prophylactic antibiotics for opportunistic infections Consider bronchoscopy, lung biopsy	If improves to Baseline: Taper steroids over at least 6 weeks If not improving after 48 hours or worsening: Add additional immunosuppression (for example, infliximab, cyclophosphamide, IV immunoglobulin, or mycophenolate mofetil) Permanently discontinue IMP
Hepatic irAEs		
Grade of Liver Test Elevation (NCI-CTCAE v4.03)	Management	Follow-up
Grade 1 Grade 1 AST or ALT > ULN to 3.0 x ULN and / or total bilirubin > ULN to 1.5 x ULN	Continue MSB0011359C therapy	Continue liver function monitoring If worsens: Treat as Grade 2 or 3 to 4
Grade 2 AST or ALT > 3.0 to ≤ 5 x ULN and / or total bilirubin > 1.5 to ≤ 3 x ULN For subjects with liver involvement at Baseline (Baseline AST ≤ 5.0 x ULN, ALT ≤ 5.0 x ULN, and bilirubin ≤ 3.0)	Delay MSB0011359C therapy Increase frequency of monitoring to every 3 days Continue MSB0011359C therapy	If returns to Baseline: Resume routine monitoring, resume MSB0011359C therapy If elevations persist > 5 to 7 days or worsen: 0.5 to 1 mg/kg/day methylprednisolone or oral equivalent and when LFT returns to Grade 1 or Baseline, taper steroids over at least 1 month, consider prophylactic antibiotics for opportunistic infections, and resume MSB0011359C therapy Continue liver function monitoring If worsens: Treat as Grades 3 to 4
Grades 3 to 4 AST or ALT > 5 x ULN and / or total bilirubin > 3 x ULN	Discontinue MSB0011359C therapy Increase frequency of monitoring to every 1 to 2 days	If returns to Grade 2: Taper steroids over at least 1 month If does not improve in > 3 to 5 days, worsens or rebounds:


For subjects with liver involvement at Baseline (Baseline AST \leq 5.0 \times ULN, ALT \leq 5.0 \times ULN, and bilirubin \leq 3.0)
	
1 to 2 mg/kg/day methylprednisolone IV or IV equivalent
 
Add prophylactic antibiotics for opportunistic infections
 
Consult gastroenterologist
 
Consider obtaining MRI/CT scan of liver and liver biopsy if clinically warranted
 
Delay MSB0011359C therapy
 
Increase frequency of monitoring to every 3 days
	
Add mycophenolate mofetil 1 gram (g) twice daily
 
If no response within an additional 3 to 5 days, consider other immunosuppressants per local guidelines
 
Permanently discontinue IMP
 
If returns to Baseline:
 
Resume routine monitoring, consider resuming MSB0011359C therapy
 
If elevations persist $>$ 5 to 7 days or worsen:
 
0.5 to 1 mg/kg/day methylprednisolone or oral equivalent and when LFT returns to Grade 1 or Baseline, taper steroids over at least 1 month, consider prophylactic antibiotics for opportunistic infections, and resume MSB0011359C therapy.
 
If does not improve in $>$ 3 to 5 days, worsens or rebounds:
 
Discontinue MSB0011359C therapy
 
Increase frequency of monitoring to every 1 to 2 days
 
1 to 2 mg/kg/day methylprednisolone IV or IV equivalent
 
Add prophylactic antibiotics for opportunistic infections
 
Consult gastroenterologist
 
Consider obtaining MRI/CT scan of liver and liver biopsy if clinically warranted
 
If does not improve in $>$ 3 to 5 days, worsens or rebounds:
 
Add mycophenolate mofetil 1 gram (g) twice daily
 
If no response within an additional 3 to 5 days, consider other immunosuppressants per local guidelines
 
Permanently discontinue IMP

--	--	---

Cardiac irAEs		
Myocarditis	Management	Follow-up
New onset of cardiac signs or symptoms and / or new laboratory cardiac biomarker elevations (eg, troponin, creatine kinase-MB, brain natriuretic peptide) or cardiac imaging abnormalities suggestive of myocarditis	
Withhold MSB0011359C therapy.
 
Hospitalize.
 
In the presence of life-threatening cardiac decompensation, consider transfer to a facility experienced in advanced heart failure and arrhythmia management.
 
Cardiology consult to establish etiology and rule out immune-mediated myocarditis.
 
Guideline based supportive treatment as per cardiology consult.^a
 
Consider myocardial biopsy if recommended per cardiology consult.
	
If symptoms improve and immune-mediated etiology is ruled out, re-start MSB0011359C therapy.
 
If symptoms do not improve/worsen, viral myocarditis is excluded, and immune-mediated etiology is suspected or confirmed following cardiology consult, manage as immune-mediated myocarditis.

Immune-mediated myocarditis	
Permanently discontinue MSB0011359C.
 
Guideline based supportive treatment as appropriate as per cardiology consult.^a
 
Methylprednisolone 1 to 2 mg/kg/day.
	
Once improving, taper steroids over at least 1 month and add prophylactic antibiotics for opportunistic infections.
 
If no improvement or worsening, consider additional immunosuppressants (eg, azathioprine, cyclosporine A).

^a Local guidelines, or eg, European Society of Cardiology or American Heart Association guidelines
 
European Society of Cardiology guidelines website: https://www.escardio.org/Guidelines/Clinical-Practice-Guidelines
 
American Heart Association guidelines website:
 
http://professional.heart.org/professional/GuidelinesStatements/searchresults.jsp?q=&y=&t=1001
		

Endocrine irAEs		
Endocrine Disorder	Management	Follow-up
Asymptomatic TSH abnormality	Continue MSB0011359C therapy If TSH < 0.5 x LLN, or TSH > 2 x ULN, or consistently out of range in 2 subsequent measurements: include T4 at subsequent cycles as clinically indicated; consider endocrinology consult	
Symptomatic endocrinopathy	Evaluate endocrine function Consider pituitary scan Symptomatic with abnormal laboratory / pituitary scan: Delay MSB0011359C therapy 1 to 2 mg/kg/day methylprednisolone IV or by mouth equivalent Initiate appropriate hormone therapy No abnormal laboratory / pituitary MRI scan but symptoms persist: Repeat laboratories in 1 to 3 weeks / MRI in 1 month	If improves (with or without hormone replacement): Taper steroids over at least 1 month and consider prophylactic antibiotics for opportunistic infections Resume MSB0011359C therapy Subjects with adrenal insufficiency may need to continue steroids with mineralocorticoid component
Suspicion of adrenal crisis (for example, severe dehydration, hypotension, shock out of proportion to current illness)	Delay or discontinue MSB0011359C therapy Rule out sepsis Stress dose of IV steroids with mineralocorticoid activity IV fluids Consult endocrinologist If adrenal crisis ruled out, then treat as above for symptomatic endocrinopathy	
Renal irAEs		
Renal Disorder	Management	Follow-up
Grade 1 or Grade 2	Repeat renal function laboratory tests / urine sediment every 2 to 3 days Stop treatment until return to baseline	
Renal dysfunction / immune-related nephritis	Evaluate renal function Consider biopsy to confirm nephritis and immune-related inflammatory process	If returns to Grade 2: Taper steroids over at least 1 month

	
Discontinue subject from MSB0011359C therapy
 
1 to 2 mg/kg/day methylprednisolone IV or IV equivalent
 
Add prophylactic antibiotics for opportunistic infections
	
If does not improve in > 3 to 5 days, worsens or rebounds:
 
Add mycophenolate mofetil 1 gram (g) twice daily
 
If no response within an additional 3 to 5 days, consider other immunosuppressants per local guidelines

--	---	---

ADL = activities of daily living; ALT = alanine aminotransferase; AST = aspartate aminotransferase; CT = computed tomography; irAE = immune-related adverse event; IV = intravenous; LFT = liver function test; LLN = lower limit of normal; MRI = magnetic resonance imaging; NCI-CTCAE = National Cancer Institute-Common Terminology Criteria for Adverse Events; T4 = free thyroxine; TSH = thyroid-stimulating hormone; ULN = upper limit of normal.

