3.5.2 Immune-related Adverse Events / Autoimmune Disorders

Immune-related AEs are AESIs.

The following irAEs are important identified risks for MSB0011359C.

- Immune-related pneumonitis
- Immune-related hepatitis
- Immune-related colitis
- Immune-related nephritis and renal dysfunction
- Immune-related endocrinopathies (thyroid disorders, adrenal insufficiency, type 1 diabetes mellitus, pituitary disorders)
- Immune-related rash
- Other immune-related events (myositis, myocarditis, encephalitis)

The following irAEs are important potential risks for MSB0011359C:

- Guillain-Barré syndrome
- Uveitis
- Pancreatitis
- Myasthenia gravis/myasthenic syndrome

Immune-related AEs / autoimmune disorders are events that are related to the pharmacology of checkpoint inhibitors and can be explained by an immune-phenomenon after other etiologies have been ruled out. Relevant clinical safety experience has been generated with the parent anti-PD-L1 avelumab antibody.

- As of 05 November 2014, a cumulative review revealed 56 cases of potential irAEs out of 480 subjects (11.7%) treated in the dose-expansion part of Trial EMR 100070-001 and 4 cases out of 50 subjects (8.0%) treated in the dose-escalation part of Trial EMR 100070-001. A

customized Medical Dictionary for Regulatory Activities (MedDRA) query was used for data retrieval from the clinical database with predefined Preferred Terms of potential irAEs.

- Of 69 potential irAEs reported, 13 were SAEs (18.8%) and 56 were nonserious AEs (81.1%). In the majority of the cases, there was a plausible temporal association between the event onset and the drug administration. Of these 69 events, 46 events (66.7%) were assessed as treatment-related by the Investigator and 23 events (33.3%) were assessed as not treatment-related by the Investigator.
- Twenty-six events were assessed as Grade 1, 29 events as Grade 2, 11 events as Grade 3, 2 events as Grade 4, and 1 event (pneumonitis) as Grade 5 (note: 2 more events of autoimmune hepatitis had a fatal outcome; however, they were assessed as Grade 3 with a subsequent fatal liver failure).
- Based on the irAE cases that have been observed with avelumab, all trial Investigators will be trained to be made aware of the frequency and severity of the observed events and to proactively administer steroid treatment for any suspicion of irAEs.

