#### 15.2.3.2 Immune Related Adverse Events

Immune-related adverse events (irAEs) will be identified programmatically. AEs which satisfy all of the following criteria will be flagged as immune-related:

- 1) The AE preferred term matches a preferred term on the list of pre-selected MedDRA terms.
- 2) The AE onset or worsening occurs after the first study drug administration and no more than 90 days after last dose , or the earliest date of subsequent anticancer therapy minus 1 day, whichever occurs first
- 3) On the AE eCRF page, the question “Were Corticosteroids, Immunosuppressants, or hormonal therapy (e.g. Thyroid) applied?” has the answer “Yes” selected.
- 4) On the imAE eCRF page, either:

- a. The question “Does any of the following provide a clear etiology for the event?” has the answer “No” selected, indicating that the AE is not attributable to underlying cancer disease/PD, prior or concomitant medications/procedures, nor another medical condition such as an infection or pre-existing disease.

OR

- b. The imAE eCRF indicates that a biopsy was performed and the question “Is the histopathology/biopsy consistent with an immune-mediated event?” has the answer “Yes” selected.

In the case that criteria (1) through (3) are met, and entries for condition (4) are missing, the following rules will be applied:

- If the answer to “Does any of the following provide a clear etiology for the event?” (4a) is missing, the event will be considered as irAE (irrespective of biopsy results).
- If the answer to “Is the histopathology/biopsy consistent with an immune-mediated event?” (4b) is missing, or if no biopsy was performed, and condition (4a) is not satisfied (i.e. “Yes” is selected as the answer to the question “Does any of the following provide a clear etiology for the event?”), the event will be considered as a non-irAE.

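### For persistent Grade 2 colitis and liver test elevation, the Section 6.5.4.3 list and Table 7 give different steroid and study-drug instructions, and no text says which governs

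*Protocol*

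**What the plan says.** Section 6.5.4.3 of the protocol opens with three lines by grade. The first allows symptom control or a moderate steroid dose for lower-grade events, with closer follow-up. The second covers lower-grade events that do not resolve: "Grade 1 to 2 (persistent): manage similar to high grade AE (Grade 3 to 4" (the closing bracket follows in the source). The third, on severe events, is "Grade 3 to 4: treat with high-dose corticosteroids".

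After the list, the section adds that "Treatment of irAEs should follow guidelines set forth in" Table 7.

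Table 7 has its own steps for events that persist. For Grade 2 diarrhea or colitis: "If persists > 5 to 7 days or recur: 0.5 to 1 mg/kg/day methylprednisolone or equivalent". For Grade 2 liver test elevation: "If elevations persist > 5 to 7 days or worsen: 0.5 to 1 mg/kg/day methylprednisolone or oral equivalent". Both entries go on to a steroid taper and resumption of study drug once the event has improved.

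Section 3.5.2, in the benefit-risk part of the protocol, says that investigators will be trained to "proactively administer steroid treatment for any suspicion of irAEs". The same section refers the reader to Section 6.5.4.3 for medical management.

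Section 5.1.7.2 says that for certain immune-related reactions the Table 7 criteria may take the place of that section, and several of its entries send the reader to Table 7.

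**The concern.** The list and the table sit in one safety section and respond to the same trigger, a lower-grade event that does not resolve. A site that applies the list to a persistent Grade 2 colitis goes to the Grade 3 to 4 instruction. A site that applies the Grade 2 row of Table 7 uses the lower steroid range and plans to restart study drug. Immune-related colitis and hepatitis are both named in Section 3.5.2 as important identified risks, and the protocol plans for approximately 220 sites. Whether to stop or restart study drug in these events should not depend on which lines a site reads first.

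The training sentence in Section 3.5.2 raises a smaller question: whether steroids begin at suspicion, or only after the symptomatic or monitoring steps with which Table 7 begins.

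**Working it through.** The point depends on no sample size, power or error rate. The check sets the texts side by side. Doses are methylprednisolone in mg/kg/day.

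| Event in Table 7 | Step on persistence | Grade 3 to 4 row | Compared with the list |
|---|---|---|---|
| Grade 2 diarrhea/colitis, > 5 to 7 days | 0.5 to 1, then resume | 1 to 2, discontinue | Steroid range and study drug both differ |
| Grade 2 liver tests, no baseline liver involvement, > 5 to 7 days | 0.5 to 1, then resume | 1 to 2, discontinue | Steroid range and study drug both differ |
| Grade 1 diarrhea/colitis; Grade 1 liver tests | None; action only on worsening | As above | List escalates, table does not |
| Grade 1 to 2 rash, > 1 to 2 weeks | Consider 0.5 to 1, resume | 1 to 2; delay or discontinue, resumption allowed on improvement with two named exceptions | Lower range is optional; study drug not opposite |
| Grade 2 pneumonitis, not improving after 2 weeks | Moves to the Grade 3 to 4 row, permanent discontinuation | 2 to 4, discontinue | Agrees |
| Grade 2 colitis persisting > 3 to 5 days on oral steroids | Moves to the Grade 3 to 4 row | 1 to 2, discontinue | Agrees, as a second step |
| Liver tests with baseline liver involvement | Grade 2: continue drug, act on worsening | Delay first; 0.5 to 1 if persistent, resumption possible | The resume-versus-discontinue conflict does not arise at this step |

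**Steroid range.** For the first two rows the ratio of the Grade 2 persistence range to the Grade 3 to 4 range is 0.5 / 1 = 0.5 at the lower end and 1 / 2 = 0.5 at the upper end. The two ranges share the value 1 mg/kg/day, so the doses given need not differ.

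**Study drug.** The instructions are opposite, resume against discontinue, in those two rows only. The list itself says nothing about study drug. Discontinuation follows from reading its phrase about managing the event like a high-grade one together with the Grade 3 to 4 rows of Table 7.

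**When steroids start.** Table 7 opens Grade 1 diarrhea/colitis with symptomatic treatment and study drug continued. It opens Grade 2 diarrhea/colitis with symptomatic treatment and study drug delayed, and Grade 1 liver test elevation with study drug continued under monitoring. None of these first steps includes a steroid. The Section 3.5.2 sentence, read literally, would start one at suspicion. It gives no grade, dose or continuation rule.

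**Which text governs.** The sentence in Section 6.5.4.3 directs sites to Table 7 but follows the list without limiting it. The provision in Section 5.1.7.2 lets Table 7 displace Section 5.1.7.2, not the list in Section 6.5.4.3. Section 3.5.2 refers to Section 6.5.4.3, which contains both the list and the table. No text ranks the list below the table.

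**The case against.** The strongest reply is that Table 7 is plainly the working text. The list is introduced as a summary of what treatment mainly depends on, the next sentence sends sites to the table, and Section 5.1.7.2 does so repeatedly. A site must also open Table 7 to learn that Grade 3 to 4 means discontinuation, and the persistent Grade 2 instruction stands in the adjacent row. This makes the intent easy to guess and opposite action less likely. It does not remove the conflicting line or say that the table prevails over it.

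A second reply is that sites do not decide alone. Section 5.5.1 requires consultation with the Medical Monitor after two or more consecutive doses are missed for medical reasons. With dosing every 14 days, a taper of at least one month (about 30 days; 30 / 14 = 2.1) would normally reach that if resumption waits for the taper. Section 5.1.7.2 also brings unresolved Grade 2 reactions to the Medical Monitor. This is a real safeguard, but it does not tell the Medical Monitor which instruction applies.

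Three stronger readings are tempting, and the documents do not support them.

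- A reader might infer that the conflict covers all persistent Grade 1 to 2 events, and might size it from the avelumab counts in Section 3.5.2: 26 + 29 = 55 of 69 potential events, or 80%, were Grade 1 or 2. Those counts span all organs, 23 of the 69 were judged unrelated to treatment, and nothing says how many persisted or were gastrointestinal or hepatic.
- A reader might infer an effect on confirmed response through altered exposure. Nothing in the documents allows that to be shown or sized.
- A reader might infer that reported immune-related rates are distorted, because SAP Section 15.2.3.2 counts an event only if the eCRF question "Were Corticosteroids, Immunosuppressants, or hormonal therapy (e.g. Thyroid) applied" is answered yes. SAP Sections 3 and 6.1 cancel the addendum and its analyses, and Section 7 states that there will be no final analysis. The completed study report used a separate analysis plan that is not among these documents. Requiring treatment in the case definition is also a debatable choice rather than an error.

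**Conclusion.** The inconsistency stands, in a narrow form. At the first persistence step, Grade 2 diarrhea/colitis and Grade 2 liver test elevation without baseline liver involvement have two instructions. They differ in steroid range (two-fold at each end, meeting at 1 mg/kg/day) and, once the list is read with the Grade 3 to 4 rows, in whether study drug is resumed or discontinued. Persistent Grade 1 gastrointestinal and hepatic events are escalated by the list and not by Table 7. The Section 3.5.2 sentence disagrees with Table 7 only on when steroids start; a reader might take it to bear on continuation, but it says nothing about that.

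The conclusion assumes that the list means what it says about persistent events and that Table 7 was extracted with its rows intact. How many subjects are affected cannot be estimated from the documents. This is a subject-safety wording error, and no trial statistic rests on it.

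**What to change.** Reconcile the list in Section 6.5.4.3, the persistence steps in Table 7 and the training sentence in Section 3.5.2, so that each organ system and grade has one instruction on steroid use and one on study drug. State which text governs, and remove or align the lines that conflict with it. If Table 7 is meant to prevail, say so in Section 6.5.4.3 itself. The sponsor's safety physicians decide the content; no dose or continuation rule is proposed here.

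The cost is a change of protocol wording and matching site training material. The stated main purpose of Version 7.2 was to update the risk classification and risk minimization measures, so the correction falls within the scope of that revision. No change to data collection or to the SAP is needed.
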